#### 5.6 Analyses of Secondary Outcome Measures

Analyses of pre-specified secondary clinic-level outcomes (Table 2, Section 4.3) will use the same analytic approach as for the primary Objective 1 outcome, and analyses of pre-specified

secondary patient-level outcomes will use the same analytic approach as for the primary Objective 2 outcome, using the appropriate link function (e.g. logit for binary measures). In addition, patient-level versions of the clinic-level implementation outcomes (e.g., number of days of OUD medication treatment) will be analyzed at a patient level among the Objective 2 sample (Objective 2 sample, see Shell Table 2; Section 10.2).

Note that unless otherwise specified, analyses will be adjusted for the baseline measure of the respective outcome being considered; exceptions are that binary or categorical outcomes derived from continuous measures will adjust for the continuous version of the measure (e.g., the binary variable of “Any acute care”) and that the patient-level binary versions of the initiation and retention measures described in in Table 2 (Section 4.3) will adjust for the baseline number of days of OUD treatment.

## 5.7 Effect Modification and Subgroup Analyses

### 5.7.1 Objective 1 Primary Implementation Outcome

Given the NIH requirement to perform subgroup analyses of the primary (Objective 1) outcome on the basis of sex, race and ethnicity, and the importance of understanding how the MA Model performs in individuals < 26 years, we plan to conduct analyses of subgroups based on: age (< 26 vs older), where age is calculated at the eligible visit closest to randomization, prioritizing any pre-randomization visits; sex; and race/ethnicity (Hispanic, Non-Hispanic White, Non-Hispanic Black, Non-Hispanic Asian, Other). We note that race and ethnicity are combined into a single variable, because in some HCS race is not documented if the patient reports ethnicity as Hispanic. An interaction term between demographic subgroup and treatment assignment can be used to evaluate whether the demographic factor moderates the implementation effect. Any such comparisons will likely be underpowered and must be interpreted with caution. The original Massachusetts studies observed that patients who were male or Black or Hispanic were less likely to engage in PC treatment of OUD with the MA Model, compared to female and white patients, respectively, but no differences were observed across age groups. As a result, PROUD investigators hypothesize that the intervention will result in smaller increases in OUD medication treatment in patients who are male or non-Hispanic Black or Hispanic but hypothesize no differences across age groups.

For each subgroup of interest, we will define the Objective 1 outcome measure among individuals within that subgroup as the number of patient-days of OUD treatment among individuals in that subgroup who were seen in the clinic during the 2 years after randomization, scaled by the total number of patients seen in the clinic (within that subgroup) during that time period. We denote the outcome for clinic  $i$  at HCS  $j$  among subgroup  $g$  as  $y_{ijg}$ .

As a concrete example, here we write down the model for the effect modification analysis for age group. Let  $g$  be an indicator variable that takes the value 1 if a person is < 26 and takes the value 0 if a person is 26 years or older. We plan to adapt the model for the primary analysis as follows:

$$y_{ijg} = \alpha_0 + \alpha_1 g + \beta_0 trt_{ij} + \beta_1 trt_{ij} g + \gamma * z_{ijg} + \theta_j + \epsilon_{ijg}$$

where

- $y_{ijg}$  is the age-group specific Objective 1 outcome measure for clinic  $i$  at HCS  $j$  (defined above),
- $trt_{ij}$  is the treatment indicator (PROUD intervention) for clinic  $i$  at HCS  $j$ ,
- $z_{ijg}$  is the age-group specific Objective 1 outcome measure for the two years prior to randomization (hereafter baseline) for clinic  $i$  at HCS  $j$ ,
- $\theta_j$  is the random effect for HCS  $j$  and is distributed  $N(0, \sigma_\theta^2)$ , and

- $\epsilon_{ijg}$  is the error term for clinic  $i$  at HCS  $j$  and is distributed  $N(0, \sigma_{\epsilon}^2)$ .

We will test whether the effect of the PROUD intervention differs across age groups by testing whether the term  $\beta_1$  differs from zero using an F test. We will also estimate age-group specific intervention effects (e.g.,  $\beta_0$  for individuals of age 26 or older and  $\beta_0 + \beta_1$  for individuals  $< 26$ ). Subgroup-specific intervention effects will be tested by using a one-tailed test, consistent with the primary (i.e., un-stratified) analysis of the Objective 1 outcome. The same modeling approach will be applied for analyses of gender. If race/ethnicity is a categorical variable with more than 2 categories, we will evaluate whether the intervention effect differs across any of the racial/ethnic groups (i.e., if effect modification is present) with an omnibus (overall) test. In addition, per our hypotheses above, we will test for a difference in outcomes between non-Hispanic Black patients and Hispanic patients, each as compared to white patients. Again, as discussed above such comparisons will likely be underpowered and should be interpreted with caution.

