8.4.1 Sociodemographic Measures

Sociodemographic characteristics available for this study include: age at randomization, sex as documented in the EHR (male, female, other, unknown); race/ethnicity (Asian, Black or African American (non-Hispanic), Hispanic, White (non-Hispanic), American Indian/Alaska Native, Native Hawaiian or other Pacific Islander, other, more than one, unknown); zip code; and type of insurance (uninsured, self-pay, state subsidized, private insurance, Medicare). Details of the covariates may be refined based on ongoing Phase 1 analyses and preliminary (3 year “baseline” period) trial analyses will be included in the SAP.

Table 8. Weekly NCM Reports to TA Team

Number of patients:

- Screened by NCM*
- New patient assessments*
- New patients to the clinic
- New patients to the health system
- Buprenorphine inductions*
- Started on injectable naltrexone*
- Follow-up visits per week
- Total with NCM phone or in-person visits per week
- Lost to follow-up (reason, etc.)
- Unexpected urine drug tests
- (%) contacted within 7 days
- Deaths and cause of death
- Re-engaged after left OUD care

* per week and to date

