### **2.3 Pre-randomization Period**

The pre-randomization period is defined as the period 3 years prior to randomization through study day 0 (randomization date), except at one health system that changed EHR systems where the pre-randomization period is limited to 2.8 years. For simplicity, throughout the SAP this pre-randomization period is referred to as 3 years. The pre-randomization period is used to define the Objective 2 primary sample. Including the randomization date in the pre-randomization period is appropriate because health systems were notified of their randomization status the day after the randomization date.

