### **2.4 Follow-up or “Post-randomization” Period**

Unless otherwise specified, the follow-up period is defined as the period from study day 1 to 2 years after the randomization date (or 1.5 years for one health system that randomized 6 months late). For simplicity, throughout the SAP this follow-up (“post-randomization”) period is referred to as 2 years.

[figure not shown]

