### 5.7.2 Objective 2 Primary Effectiveness Outcome

We plan to conduct analyses of subgroups based on: age ( $< 26$  vs older) at randomization; sex; race and ethnicity (Hispanic, Non-Hispanic White, Non-Hispanic Black, Non-Hispanic Asian, Other), using similar subgroups as Objective 1. If one of the subgroups is small (fewer than 5% of patients in the sample), we will consider excluding that category or combining with the “Other” category. To examine whether the treatment effect may differ across groups, we plan to apply the same analytic approach as for the primary analysis of the Objective 2 outcome, in which we will additionally include an interaction term between the categorical subgroup variable of interest and the treatment effect term. As above, such comparisons are expected to be underpowered and will be interpreted cautiously. To aid in the interpretation of potential subgroup-specific effects, we plan to additionally conduct analyses of these subgroups for the patient-level treatment outcome of number of days of OUD medication treatment.

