Requiring 2+ orders/procedure codes to define treatment and omitting the last order			
Altering allowable gap to define continuous episodes of OUD treatment (main analysis allowable gap=7 days)			
2-day allowable gap			
5-day allowable gap			
10-day allowable gap			
Seen in the clinic pre-randomization			
OUD pre-randomization			
No OUD pre-randomization			
Patients new to the clinic post randomization			
Altering assignment of clinic to be the clinic with the most visits post randomization			
a Defined as having a medication order or procedure code for buprenorphine formulations that are indicated for OUD or having a medication order or procedure code for injectable naltrexone and 2+ visits with an OUD or OD diagnosis code (diagnosis codes can be during the 2-years pre or 2-years post randomization) b Mean difference in the primary outcome comparing clinics randomized to the PROUD intervention vs. clinics randomized to usual care, estimated from a random effects model adjusted for the primary outcome measure at baseline (two years prior to randomization) c Adjusted for {2 covariates determined from lasso regression} and baseline OUD treatment in random effects model			

Supplementary Table 6. Implementation of OUD medication treatment at the clinic-level in the 2 years post randomization stratified by patient characteristics, Primary Care Opioid Use Disorders Treatment (PROUD) trial			
	6 intervention clinics	6 usual care clinics	P value b
	Mean (SD) patient years of treatment across clinics per 10,000 patients in the subgroup		
Age at eligible visit closest to randomization a			
<26			
≥ 26			
Sex			
Female			
Male			
Race/Ethnicity			
Hispanic			
Non-Hispanic			
White			
Black			
Asian			
Other			

a Eligible primary care visits closest to and prior to randomization. If no eligible visits prior to randomization, post-randomization visit closest to randomization date was chosen.

b P values are presented for omnibus tests evaluating whether there is any difference in the intervention effect across subgroups, as well as for differences in subgroup-specific intervention effects, obtained from a linear mixed model with interaction terms between the intervention group and the subgroup

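### The under-26 subgroup takes age at a visit in Objective 1 but age at randomization in Objective 2, so some patients can change age group between the two analyses

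*SAP*

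**What the plan says.** For Objective 1, SAP 5.7.1 splits patients at age 26, "where age is calculated at the eligible visit closest to randomization, prioritizing any pre-randomization visits". The footnote to Supplementary Table 6 (SAP 10.1) covers patients who are new during follow-up: "If no eligible visits prior to randomization, post-randomization visit closest to randomization date was chosen".

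Two definitions set how far that visit can lie from randomization. SAP 2.3 states: "The pre-randomization period is defined as the period 3 years prior to randomization through study day 0 (randomization date"; one health system has 2.8 years. SAP 2.4 states: "the follow-up period is defined as the period from study day 1 to 2 years after the randomization date"; one health system has 1.5 years.

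For Objective 2, SAP 5.7.2 takes the age split (<26 "vs older) at randomization; sex; race and ethnicity"), and describes this as "using similar subgroups as Objective 1". The covariate lists in SAP 5.4.1 and 5.5.2 also use age at randomization. The list in 5.5.2 serves the secondary sample, which includes patients never seen in the health system before randomization. Protocol 8.4.1 reads: "Sociodemographic characteristics available for this study include: age at randomization". Protocol Table 4 lists date of birth among the data obtained from each site.

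No section explains why the two objectives use different age anchors.

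**The concern.** The two objectives report an under-26 subgroup with the same label but a different rule for who belongs to it. Protocol 4.3.2 singles out this age group as a gap in the literature, and Protocol Tables 11 and 15 plan manuscripts on primary and secondary outcomes by age. Readers will therefore set the two results side by side.

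Two things follow from the visit-based rule.

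- A patient's age can be out of date by the time the outcome is measured. The outcome accrues only after randomization.
- For patients with no earlier visit, the subgroup depends on when they first attend after randomization. SAP 5.5.2 prefers covariates fixed before randomization, so that the intervention cannot affect them. SAP 5.5.1 expects that the intervention may attract new patients. Age at randomization meets that preference for everyone; age at first visit does not.

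What is at stake is the consistency and interpretation of a secondary, pre-planned subgroup analysis, not the trial's main conclusions.

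**Working it through.** **Can a patient be classified in opposite groups?** Yes. Take a patient aged 25.5 at the last eligible visit, 1 year before randomization. Under 5.7.1 the patient is <26. Age at randomization is 25.5 + 1.0 = 26.5, so under 5.7.2 the patient is older. The reverse can happen only for someone whose trial-clinic visits are all after randomization. Such a patient is not in the Objective 2 primary sample, but can be in its secondary sample.

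**How often?** The plan gives no figure for this subgroup, so there is none to reproduce. I estimated the size by simulation (2,000,000 patients per scenario).

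Inputs from Protocol Table 2:
- share of patients aged 16–25, p: 8.55% to 19.13% across sites;
- share with an earlier visit, q: 0.60 or 0.88, using the row for patients seen in 2016 who were also seen in 2014–2015 (60.3% to 88.2%) as a proxy.

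Assumptions not in the documents:
- ages spread evenly around 26;
- mean lag L from last pre-randomization visit to randomization of about 0.25 to 1.25 years, cut at 3 years;
- lead from randomization to first visit for new patients exponential with scale 0.75 years, cut at 2 years.

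Let m1 be the share of the Objective 1 '<26' group who are 26 or older at randomization, and m2 the share of its '≥26' group who are under 26 at randomization. A true interaction keeps the fraction 1 − m1 − m2 of its size.

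| p | q | L (years) | Grouped differently | m1 | m2 | Interaction kept |
|---|---|---|---|---|---|---|
| 8.55% | 0.60 | 0.25 | 0.33% | 1.5% | 0.22% | 98.2% |
| 8.55% | 0.60 | 1.25 | 0.85% | 7.7% | 0.23% | 92.1% |
| 8.55% | 0.88 | 0.25 | 0.25% | 2.2% | 0.07% | 97.7% |
| 8.55% | 0.88 | 1.25 | 1.02% | 11.1% | 0.07% | 88.8% |
| 19.13% | 0.60 | 0.25 | 0.74% | 1.5% | 0.57% | 97.9% |
| 19.13% | 0.60 | 1.26 | 1.93% | 7.7% | 0.58% | 91.7% |
| 19.13% | 0.88 | 0.25 | 0.56% | 2.3% | 0.17% | 97.6% |
| 19.13% | 0.88 | 1.25 | 2.30% | 11.1% | 0.17% | 88.7% |

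Intermediate lags (about 0.5 and 0.84 years) fall between these rows.

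**Hand check.** Over a 10-year age band, m1 ≈ q × L / 10. The lowest case is 0.60 × 0.25 / 10 = 1.5% and the highest 0.88 × 1.25 / 10 = 11%, in agreement with the table.

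**Outer bound.** If every patient's last visit were exactly 3 years before randomization, m1 would be about 3/10 = 30%. This is unrealistic, because the rule takes the closest pre-randomization visit.

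**After the change.** With age at randomization in both objectives, no patient is grouped differently and the whole interaction is kept, by construction.

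**The case against.** The case for leaving the rule alone has several parts.

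- *It is pre-specified and the same in both arms.* This stands. For patients with a pre-randomization visit, age is fixed before assignment is known, so the arm comparison is not biased. For new patients the classifying visit comes after randomization, and that protection is weaker.
- *Age at first visit may be closer to age at exposure for a new patient.* This is a fair argument for new patients. It does not explain the rule as a whole, because pre-randomization visits take priority. A returning patient keeps an age from up to 3 years earlier, even if seen again soon after randomization.
- *The protocol is not contradicted.* This stands. Protocol 8.4.1 lists age at randomization among the available characteristics and lets the SAP refine covariate details. Protocol 4.3.2 and 11.3.4 set the cut-off at 26 without an anchor date.
- *The two samples differ anyway.* This stands. The Objective 2 primary sample needs an OUD diagnosis before randomization and age at least 16 two years before it, hence at least 18 at randomization. Objective 1 takes all eligible patients from age 16 at a visit. SAP 5.7.2 claims only similarity.
- *The comparisons are already labelled underpowered.* This stands and limits the importance of the point. It is not a reason to keep an unexplained difference.

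A reader might infer that the Objective 1 age contrast is diluted by about 10%. Protocol Table 2 invites this: 173,166 of 287,420 three-year patients (60%) were seen in the latest year. Assuming lags of 0.4 years for them and 1.8 years for the rest gives 0.60 × 0.4 + 0.40 × 1.8 = 0.96 years, or about 10% of a 10-year band. The documents do not support that reading. Those lags appear nowhere in them. The 5.7.1 outcome counts only patients "who were seen in the clinic during the 2 years after randomization, scaled by the total number of patients seen in the clinic", so people who never return contribute nothing, and those who do return probably have shorter lags. Dilution also needs a true interaction. SAP 5.7.1 hypothesizes no difference by age, although Protocol 4.3.2 hypothesizes a smaller increase in patients under 26.

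A reader might also infer that the mismatch undermines the treatment-days analysis that SAP 5.7.2 adds to help interpret its subgroup results. It does not: that analysis uses the Objective 2 subgroups throughout.

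**Conclusion.** This is a minor but real inconsistency in definition. The age anchors differ without explanation. A patient in both analyses can fall in opposite age groups, and new patients' membership depends on post-randomization visit timing.

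The size is small. About 0.25% to 2.3% of patients would be grouped differently under the two rules. A true age interaction, if there is one, would lose about 2% to 11% of its size; if there is none, there is nothing to attenuate. These ranges rest on the assumed visit lags, the even spread of ages and the Table 2 proxy. The attenuation formula also treats misclassified patients as responding like the average of their true group. Most of them are just past 26, so if the effect changes gradually with age the loss would be smaller.

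The primary analyses of both objectives do not use this subgroup and are unaffected.

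**What to change.** In SAP 5.7.1 and the footnote to Supplementary Table 6, replace the visit-based rule with age at the health system's randomization date, computed from date of birth, for every patient.

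Check the age rows of the Objective 1 Table 1a. One of its footnotes refers to the eligible visit closest to and before randomization, and in the text available it cannot be seen which row this belongs to. If it is age, use the same anchor there, so that the Objective 1 paper is consistent within itself.

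The cost is one sentence, one derived variable and a footnote. No patient is lost from the subgroup analysis: someone who reaches 16 only during follow-up is still under 26 at randomization. Eligibility stays visit-based.

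If visit-based age is preferred, state the reason and report how many patients would change group under age at randomization. Either way, the text should say that the two objectives' under-26 groups still differ in OUD status and minimum age.

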#### 6.1.1 Data-generation and Analysis Model

In our power simulation, there were 6 HCSs and 2 clinics within each HCS (one clinic assigned to the intervention and one to UPC), making 12 clinics in all.

The outcome variable for each clinic is *Treated Days per Patient Seen*, which with actual data, we would calculate by dividing the total number of treated days at the clinic during 2 years of follow-up by the total number of unique patients seen by the clinic during that same time period. To evaluate power under an analysis approach that adjusts for the baseline value of the outcome, we used Phase 1 data to calculate an approximation of the magnitude of the association between the number of OUD-treated days per patient seen pre- and post-randomization. Using the analytic model specified in Equation (1) would require four years of data for this estimation, however only three years of data are available from Phase 1 (FYs 2014, 2015 and 2016). Thus, data were simulated in a recursive fashion using an autoregressive lag-1 approach.

Step 1: Estimate via regression the relationship between the number of OUD-treated days per patient seen in the last two years of Phase 1 data (2015-2016) and the same measure for the first two years of the Phase 1 data (2014-2015). Letting  $j$  index HCS and  $i$  index clinics within an HCS, this corresponds to regression of the outcome for 2015-2016 on 2014-2015 (see Section 6.1.2). That is, model

$$y_{ij\langle 2015-2016 \rangle} \sim \mu + \rho y_{ij\langle 2014-2015 \rangle}. \quad (2)$$

For this model, a random effect capturing the correlation of clinics from the same health care system was *not* included (see Section 6.1.2). The parameter  $\rho$  captures the association between the number of treated days per patient seen across consecutive years, and the parameter  $\mu$  captures the mean number of treated days per patient seen if no individuals were treated for OUD in the previous year. Let  $\hat{\mu}$  and  $\hat{\rho}$  denote the estimates from the above model.

Step 2: Using this estimated regression model ( $\hat{\mu}, \hat{\rho}$ ), simulate the outcome measure for the next two-year period (2016-2017) for the UPC clinics (i.e.,  $i=1$ ) from

$$\hat{y}_{1j\langle 2016-2017 \rangle} = \varphi + \omega \tilde{y}_{1j\langle 2015-2016 \rangle} + \varepsilon_{1j}$$

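### The Objective 1 subgroup model in SAP 5.7.1 enters several rows per clinic without a clinic-level term, so its interaction and one-sided subgroup tests can miss their nominal error rates

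*SAP*

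**What the plan says.** SAP 5.1 analyses one value per clinic, with terms for arm and baseline value, an HCS random intercept and a residual. There are two clinics in each of six systems, "making 12 clinics in all" (SAP 6.1.1).

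SAP 5.7.1 recomputes the outcome separately for each subgroup in each clinic and fits all the values together. It says "We plan to adapt the model for the primary analysis as follows":

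y_ijg = α0 + α1·g + β0·trt_ij + β1·trt_ij·g + γ·z_ijg + θ_j + ε_ijg

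In the age model, which is the only one written out, g "takes the value 1 if a person is < 26 and takes the value 0 if a person is 26 years or older". The same approach is to be used for gender. The other factor is listed as "race/ethnicity (Hispanic, Non-Hispanic White, Non-Hispanic Black, Non-Hispanic Asian, Other", with an omnibus test if there are more than two categories.

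Two random terms are defined. θ_j "is the random effect for HCS", and ε_ijg "is the error term for clinic", with one common variance. There is no clinic term, no correlation between rows from the same clinic, and no stated degrees-of-freedom (df) method.

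Two kinds of test follow. The SAP says "We will test whether the effect of the PROUD intervention differs across age groups", using an F test of β1. It also says "Subgroup-specific intervention effects will be tested by using a one-tailed test". The only caution is that power is likely to be low.

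**The concern.** With one row per clinic, the residual in SAP 5.1 is the clinic-level error, so that structure is complete. Once a clinic supplies two or five rows, anything shared by its subgroups (nurse hiring, prescriber uptake, success of implementation) becomes a correlation that the model leaves out. The omitted clinic variance goes into the residual. That is too large an error for the interaction, which is a within-clinic contrast. It is too small an error for a subgroup's arm effect, which varies only between clinics.

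The SAP gives reasons to expect such correlation:
- The HCS variance for this outcome was estimated as zero in Phase 1 (6.1.2), so θ_j cannot be relied on to carry it.
- In Table 3, the two clinics of HCS 4 had 0.021 and 0.431 treated days per patient in fiscal years 2015-2016.
- Sections 5.2.2 and 7.7 anticipate unequal implementation success.
- Section 5.3 does include clinic random intercepts for Objective 2, where clinics also supply many rows.

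At stake are the error rates of the sex and race/ethnicity analyses that the SAP ties to an NIH requirement, and of the planned comparison under and over age 26.

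**Working it through.** **1. The plan's own figure.** Table 5 gives error and power for the primary model; no error rate is given for the 5.7.1 model. The inputs are intercept 0.05, coefficient 0.94 and residual SD 0.10 (SAP 6.1.2, Table 4). Clinics were generated independently, with 3,000 runs, one-sided 5% tests and containment df. The df are 12 − (3 + 5) = 4 with baseline and 12 − (2 + 5) = 5 without.

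| Fold increase | Table 5, adjusted | Reproduced | Table 5, unadjusted | Reproduced |
|---|---|---|---|---|
| 1.00 | 5% | 5.2% | 5% | 5.9% |
| 1.18 | 49% | 47.7% | 21% | 21.0% |
| 1.30 | 84% | 83.4% | 39% | 40.9% |
| 1.42 | 98% | 97.8% | 60% | 58.8% |

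Agreement is within 2 points. Residual df would give 89% at 1.30, so containment df was used below.

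**2. Closed form, ignoring baseline.** Let σu² be the shared clinic variance, σe² the remainder, ρ = σu²/(σu² + σe²), and G the rows per clinic. After removing HCS, arm, subgroup and interaction, 5 df remain between clinics, each with expectation σe² + Gσu². Another 10(G − 1) df remain within clinics, with expectation σe². The 5.7.1 model pools them:

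[5(σe² + Gσu²) + 10(G − 1)σe²] / [5 + 10(G − 1)] = σe² + Gσu²/(2G − 1)

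The correct factor is σe² for an interaction and σe² + σu² for a subgroup effect. With total variance 1:
- G = 2, ρ = 0.5: 0.5 + 2(0.5)/3 = 0.833. The ratio of model to true variance is 0.833/0.5 = 1.67 (interaction) and 0.83 (subgroup).
- G = 2, ρ = 0.9: 0.1 + 2(0.9)/3 = 0.70. The ratios are 7.0 and 0.70.
- G = 5, ρ = 0.5: 0.5 + 5(0.5)/9 = 0.778. The ratios are 1.56 and 0.78.
- G = 5, ρ = 0.9: 0.1 + 5(0.9)/9 = 0.60. The ratios are 6.0 and 0.60.

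**3. Null simulation of the 5.7.1 model.** REML fits with baseline included, equal subgroup variances and HCS SD 0; 2,500 runs for G = 2 and 1,500 for G = 5. The df are 24 − 10 = 14 and 60 − 16 = 44. All tests are nominal 5% (the SAP states no level for the F test). Monte Carlo error near 5% is about 1 point. ρ is an assumption.

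| ρ | Interaction, 2 groups | One-sided subgroup, 2 groups | Omnibus, 5 groups | One-sided subgroup, 5 groups |
|---|---|---|---|---|
| 0 | 5.5% | 5.6-6.2% | 4.2% | 4.1-5.9% |
| 0.25 | 2.8% | 5.4-6.3% | 3.3% | 6.3% |
| 0.5 | 1.6% | 6.7-7.2% | 1.3% | 8.7-8.9% |
| 0.75 | 0.8% | 9.8-10.1% | 0.5% | 9.6-10.3% |
| 0.9 | 0.1% | 10.0-10.2% | 0.1% | 13.0-14.1% |

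An HCS SD of 1 gives similar results. A simpler balanced check, with HCS as a block and no baseline covariate, gives the following at ρ = 0.25/0.5/0.9. Two groups: interaction 3.1/1.5/0.05%, subgroup about 5.6/7.0/9.4%. Five groups: omnibus 2.6/1.2/0.03%, subgroup about 6/7.4/11%.

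**4. Unequal subgroup variances (two groups).** With subgroup SD ratios of 0.5 or 0.25 and ρ of 0.5 or 0.9, the noisier subgroup's one-sided test rejects 12-15%, the less noisy one 0-3%, and the interaction 1.0-5.8%. For age, Protocol Table 2 puts ages 16-25 at 8.55-19.13% of patients. If variance scales as 1/n (an assumption), the older-to-younger SD ratio is √(0.0855/0.9145) = 0.31 to √(0.1913/0.8087) = 0.49. With ρ from 0.25 to 0.75, the under-26 test then rejects about 9-14%. The 26-and-over test rejects 0-2% if clinic and residual SDs both scale, and 2-8% if only the residual does.

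**5. Analyses that respect the clinic.** For two groups, testing the interaction on within-clinic differences gives 4.4-6.0%. Fitting the primary model within each subgroup gives 4.1-6.9%. With unequal variances, these two analyses give 4.8-5.9%. In the balanced check, within-clinic interaction tests and per-subgroup clinic-level tests give 4.6-5.5%, including five groups.

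**The case against.** The strongest reply is that no size can be read from the documents. They give no within-clinic share for this outcome. The clinic and HCS variances in SAP 5.3 (0.055 against 0.00016) belong to the Objective 2 outcome. The 5.7.1 model adjusts for subgroup-specific baseline, and the Phase 1 coefficient was 0.94, so stable clinic differences may be largely removed. At a share of 0.1 the interaction test rejects 4.4%, and one run at 0.25 gave 3.7%. These are also secondary results for a supplementary table, the SAP already calls them underpowered, and the five-row race/ethnicity model is inferred from the category list.

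Much of this stands, and it is why every size here is conditional. It does not remove the defect. Baseline cannot absorb differences in implementation that arise after randomization. A low-power caveat does not cover one-sided tests that reject too often. The equation is a stated model, so the missing clinic term is not simply detail left for later.

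A reader might infer that the interaction test is always far too conservative and the subgroup tests always too liberal. Step 4 shows otherwise when variances differ. A reader might also infer that real subgroup differences can hardly be detected. No power loss was calculated, so that is not shown. Nor does the concern extend to an arm effect averaged over subgroups, because SAP 5.7.1 plans no such test.

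**Conclusion.** The concern holds as a conditional specification fault in SAP 5.7.1. Rows from one randomized clinic are treated as independent given HCS, under a single residual variance.

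If implementation success is shared within clinics and subgroup variances are equal, then at shares 0/0.25/0.5/0.9:
- Two groups: the interaction test rejects about 5/3/1.5/0.1%, and one-sided subgroup tests about 5/6/7/10%.
- Five groups: about 5/3/1/0.1% and 5/6/7-9/11-14%.

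If variances differ, the noisier subgroup's test rejects roughly 9-15%, the less noisy one's can be conservative, and the interaction can be near nominal. The share, the variance pattern and the 5% interaction level are assumptions. The primary Objective 1 test, with one row per clinic, is unaffected.

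**What to change.** The simpler and more robust choice with 12 clinics has two parts:
- Test interactions on within-clinic subgroup differences. For two groups this is one difference per clinic, regressed on arm and the baseline difference. For race/ethnicity, test the omnibus interaction against within-clinic error, and the Black-White and Hispanic-White contrasts as clinic-level differences.
- Obtain each subgroup-specific effect by fitting the SAP 5.1 model within that subgroup. This also handles unequal variances for the subgroup effects.

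Alternatively, add a clinic-within-HCS random intercept, or a within-clinic residual covariance across subgroups, to the 5.7.1 model and state the df method, so that interactions are tested on within-clinic error. Its error rates with 12 clinics were not checked. With separate residual variances for five groups it would have seven variance parameters (HCS, clinic and five residuals) for 60 rows, so convergence should be examined first. The five-group omnibus test under unequal variances was not checked either.

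The cost is slightly more analysis work, a revised P-value footnote to Supplementary Table 6, and fewer df for subgroup effects (4 instead of 14 or 44). No new data are needed and the primary analysis does not change.
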